**Table 3 Schedule of assessments for patients who have completed or discontinued treatment**

Evaluation	Time since last dose of IP		For details, see Section
	Weeks		
	4 ( $\pm$ 3d) a	12 ( $\pm$ 1w)	q12w $\pm$ 1w until primary DFS analysis b or until disease recurrence
Physical examination (full)	X		8.2.3
Vital signs (temperature, respiratory rate, blood pressure, and pulse)	X		8.2.4
Pregnancy test c	X	X	8.2.1
AE/SAE assessment		X d	8.3
Concomitant medications		X	6.4
WHO/ECOG performance status	At timepoints consistent with tumor assessments; at 30 and 90 days; and then at initiation of subsequent anticancer therapy e		8.2.7
Subsequent anticancer therapy f and progression assessment g	<----->		8.1
Survival status		X	8.1.3
Hematology	X	X	Table 12
Clinical chemistry	X	X	Table 11
TSH (reflex free T3 or free T4)	X	X	Table 11
Plasma samples for exploratory analyses	q12w $\pm$ 1w (preferably to coincide with time of scan)		8.7.2.1
CCI, CCI, CCI, CCI, CCI, CCI k	Sample at time of RECIST 1.1-defined disease recurrence (if applicable) To be completed q4w until PFS event following disease recurrence (ie, a DFS event), study discontinuation, or death (whichever occurs first) PRO data collection will stop at the time of primary DFS analysis		8.1.4
Health resource use (HOSPAD) l	To be completed at each hospitalization until PFS event following disease recurrence (ie, a DFS event), initiation of subsequent therapy, study discontinuation, or death (whichever occurs first)		

**Table 3 Schedule of assessments for patients who have completed or discontinued treatment**

Evaluation	Time since last dose of IP		For details, see Section
	Weeks		
	4 (± 3d) a	12 (± 1w) q12w ± 1w until primary DFS analysis b or until disease recurrence	
Disease assessment (RECIST 1.1)	Disease assessments occur q8w ± 1w until Week 48, then q12w ± 1w (relative to the date of randomization) until appearance of RECIST 1.1-defined disease recurrence or completion of the study. m,n Upon detection of RECIST 1.1-defined disease recurrence, an additional follow-up CT scan should be performed 4-8w later and evaluated using post-progression radiological criteria. o		8.1 Appendix G
Tumor biopsy sample (optional) p	At recurrence l		8.7.2.2

a Patients who discontinue treatment due to disease recurrence will continue to be followed for OS and subsequent therapy until the end of the study. See footnote k for details regarding the timing of final sample collection.

b After database lock for primary DFS analysis, all patients remaining on study will continue for OS follow-up including collection of data on safety and subsequent therapies. Plasma samples for exploratory analyses will no longer be collected. Efficacy scans will be collected in accordance with local clinical practice. See Section 6.1.3 for details.

c For women of childbearing potential only. A urine or serum pregnancy test is acceptable.

d SAEs that occur after the 90-day safety follow-up period and that the Principal Investigator deems to be significant or related to IP should be reported.

e WHO/ECOG performance status should also be collected at other site visits that the patient attends, if appropriate site staff are available to collect such information. In addition, WHO/ECOG performance status should be provided when information on subsequent anticancer therapy is provided, where possible.

f Details of any treatment for NSCLC (including surgery and radiotherapy) post the last dose of IP must be recorded in the eCRF through the completion of the study.

g Post-recurrence progression (PFS) will be assessed by the Investigator per local clinical practice (See section 8.1.1.3).

h Patients may be contacted in the week following data cut-offs to confirm survival status.

i Free T3 or free T4 will only be measured if TSH is abnormal or if there is clinical suspicion of an AE related to the endocrine system.

j For patients who discontinued treatment due to disease recurrence, the last plasma sample should be collected with the optional biopsy of recurrent tumor (if provided) at the visit 4 weeks post-last dose of IP. For patients who complete treatment, but who later experience disease recurrence, these plasma and tumor biopsy samples should be collected as close to the time of disease recurrence as possible (ie, at the time the additional follow-up scan is performed approximately 4-8 weeks after the first radiographic evidence of RECIST 1.1-defined disease recurrence).

k **CGI**

l HOSPAD module should be completed by site staff whenever the patient has attended or been admitted in to the hospital. A reminder will be provided at each clinic visit.

m On-study schedule of q12w ± 1w (relative to the date of randomization) must be followed.

- n Contrast-enhanced CT scan of the chest and abdomen (including liver and adrenal glands) is required. Brain MRI (preferred) or brain CT with IV contrast may be performed only if clinically indicated.
- o Post-progression scans will be performed per local clinical practice.
- p FFPE sample of recurrent tumor biopsy will be collected from consenting patients.
- d Day; DFS disease-free survival; ECOG Eastern Cooperative Oncology Group; eCRF Case report form; CCI [REDACTED]; FFPE Formalin-fixed paraffin-embedded; HOSPAD Hospital resource use module; IP investigational product; NSCLC non-small cell lung cancer; OS Overall survival; CCI [REDACTED]; q8w Every 8 weeks; q12w Every 12 weeks; RECIST Response Evaluation Criteria in Solid Tumors; SAE Serious adverse event; T3 Triiodothyronine; T4 Thyroxine; TSH Thyroid-stimulating hormone; WHO World Health Organization; w Week.

**Table 4 Schedule of assessments for observation period (initiated by the signing of ICF2b)**

	Up to 24 months or until RECIST 1.1-defined disease recurrence or primary DFS analysis (whichever occurs first) a	For details, see Section
ICF2bb	X	5.1
Medical history	To be collected on or by the first observation visit	8.2.2
Pregnancy test c	X	
SAEs	<----->	8.3
Subsequent anticancer therapy	<----->	8.1.3
Survival status	q12w ± 1w	8.1.3
Plasma sample for exploratory analyses c	q12w ± 1w coinciding with scans and at time of disease recurrence, or until discontinuation from the study	8.7.2.1
Disease assessment (RECIST 1.1) d	Follow-up disease assessments occur q12w ± 1w (relative to the date of surveillance completion) until appearance of RECIST 1.1-defined disease recurrence or end of the study e,f . Upon detection of disease recurrence, an additional follow-up scan should be performed 4-8w later and evaluated using post-progression radiological criteria g	8.1 Appendix G
Tumor biopsy sample (optional) h	At recurrence	8.7.2.2

a Patients in observation will adhere to this schedule of assessments until (1) completion of 24 months in observation; (2) disease recurrence; or (3) until primary DFS analysis; after which, these patients will be followed for OS (including subsequent therapy) until the end of the study.

b Written informed consent and any locally required privacy act document authorization must be obtained prior to performing any protocol-specific procedures. The procedures outlined in this table will be initiated by the signing of ICF2b.

c For women of childbearing potential only. A urine or serum pregnancy test is acceptable.

d After database lock for primary DFS analysis (See Section 6.1.3), plasma samples for exploratory analyses will no longer be collected. Scans will be collected in accordance with local practice.

e Scan schedule of q12w ± 1w (relative to the date of randomization) must be followed while a patient is in observation.

f Contrast-enhanced CT scan of the chest and abdomen (including liver and adrenal glands) is required. Brain MRI (preferred) or brain CT with IV contrast may be performed only if clinically indicated.

g Post-progression scans will be performed per local clinical practice.

h FFPE samples of recurrent tumor biopsy will be collected from consenting patients.

CT computed tomography; DFS disease-free survival; ICF2b Informed consent form 2b; IV intravenous; MRI magnetic resonance imaging; OS Overall survival; q12w Every 12 weeks; RECIST Response Evaluation Criteria in Solid Tumors; SAE Serious adverse event; w Week(s).

## 1.2 Synopsis

*From CSP v2.0 implementation at site, please use to Section 10 as a reference point for the study. This study has closed enrolment early and patients will either start open-label durvalumab or be discontinued from the study.*

*The synopsis below refers to the original study design. The objectives and endpoints have been updated for CSP v2.0. All analyses of the objectives and endpoints will be descriptive only and considered exploratory.*

### Rationale:

Up to 30% of patients with non-small cell lung cancer (NSCLC) present with surgically resectable disease (Molina et al 2008). For patients with stage II-III A and select stage III B disease, surgery and adjuvant standard of care (SoC) chemotherapy results in 5-year disease-free survival (DFS) rates of only ~40% (Wakelee et al 2017). Long-term survival is improved through administration of chemotherapy in the immediate post-operative setting (Pignon et al 2008), yet chemotherapy in the first-line metastatic setting results in no long-term survival benefit and progression-free survival (PFS) benefits of only a small number of months (Cochrane Review 2000). In contrast, immunotherapy agents have transformed the treatment landscape in the first-line setting (Garon et al 2019) and provides a rationale to conduct studies to intercept relapsing NSCLC with immunotherapy prior to the emergence of therapeutic resistance that characterizes overt metastatic disease.

There is evidence that detection of minimal residual disease (MRD) through detection of circulating tumor DNA (ctDNA) post-surgery can accurately predict recurrence (Abbosh et al 2017, Chaudhuri et al 2017). In the TRACERx study, the presence or absence of MRD was evaluated via ctDNA detection in plasma samples taken from patients who had undergone surgery for stage III NSCLC. In 13 of 14 patients who underwent surgical resection of their tumors and subsequently suffered post-operative relapse of their disease, MRD was detected via ctDNA before or at the point of clinically evident disease recurrence (through SoC imaging or presentation of symptoms) (Abbosh et al 2017). In all 12 patients who did not experience post-operative disease recurrence, MRD was not detected following surgery (Abbosh et al 2017). Detection of MRD at a time when there is no radiologic evidence of disease provides an opportunity for earlier therapeutic intervention (Abbosh et al 2018). Patients with MRD (MRD-positive [MRD+]) experience inferior recurrence-free survival compared to patients without detectable MRD (MRD-negative [MRD-]). Therefore, MRD+ patients could benefit from earlier intervention and escalation of additional adjuvant therapy (including immunotherapy); furthermore, MRD- patients (the majority of whom are cured by surgery alone) could be spared from additional treatment and the resulting unnecessary toxicity.

Immunotherapy has changed the landscape of advanced NSCLC (Martinez et al 2019). First-line treatment of metastatic NSCLC with anti-programmed cell death-1 (anti-PD-1) or anti-programmed cell death ligand 1 (anti-PD-L1) monotherapy has demonstrated an overall survival (OS) benefit compared with chemotherapy alone in patients whose tumors expressed PD-L1 (Garon et al 2019, Mok et al 2019, Reck et al 2016, Spigel et al 2019). In the second- or third-line metastatic setting, it has further been established that immune-oncologic (IO) therapy can provide clinical benefit irrespective of PD-L1 status (Rittmeyer et al 2017). However, even with these improvements, most patients will experience disease progression and ultimately die.

Durvalumab can be effective in situations of residual cancer as evidenced by improved PFS and OS observed with durvalumab versus placebo following definitive concurrent chemoradiation in the PACIFIC study (Antonia et al 2018, Gray et al 2019). Moreover, intervention with combination chemotherapy and immunotherapy versus chemotherapy alone improves PFS and OS in advanced NSCLC (Gandhi et al 2018, Gadgeel et al 2019, Paz-Ares et al 2018). These data suggest that earlier intervention with immunotherapy as adjuvant therapy following curative intent treatment could improve outcomes in early-stage NSCLC, prevent progression, and circumvent the need to expose patients to potentially more toxic chemotherapy regimens in the metastatic setting.

This study is being conducted to evaluate the efficacy and safety of durvalumab adjuvant therapy compared to placebo in patients with completely resected stage II-III NSCLC who

have undergone curative intent therapy (complete resection ± neoadjuvant and/or adjuvant therapy), and who become MRD+ during a 96-week surveillance period.

## Objectives and Endpoints

Primary objective:	Endpoint/variable:
To assess the efficacy of durvalumab compared to placebo as measured by DFS in all randomized patients	DFS in FAS (using Investigator assessments according to RECIST 1.1)
Secondary/Safety objective:	Endpoint/variable:
To assess the safety and tolerability profile of durvalumab monotherapy compared with placebo	AEs, physical examinations, vital signs, and laboratory findings
Exploratory objectives:	Endpoint/variable:
To assess the efficacy of durvalumab compared to placebo as measured by DFS in the PD-L1 TC≥1% analysis set	DFS in PD-L1 TC≥1% (using Investigator assessments according to RECIST 1.1)
To assess the efficacy of durvalumab compared to placebo on post-recurrence outcomes	PFS (using local standard practice) CCI [REDACTED] CCI [REDACTED]
To assess the efficacy of durvalumab compared to placebo as measured by OS in the PD-L1 TC≥1% analysis set and in all randomized patients	OS in PD-L1 TC≥1% and in FAS
To assess patient-reported symptoms, functioning, and HRQoL in patients treated with durvalumab compared to placebo	Change from baseline and time to deterioration in EORTC QLQ-C30 and EORTC QLQ-LC13
To investigate the relationship between a patient's baseline PD-L1 TC expression and efficacy of study treatments	IHC analysis of PD-L1 TC expression and spatial distribution within the tumor microenvironment relative to efficacy outcomes (ie, DFS, OS)
To assess the efficacy of durvalumab monotherapy to clear ctDNA compared to placebo	ctDNA endpoints, as defined by: 
 
• Best overall clearance rate (number converted at any time)
 
• Best confirmed clearance rate (as above but confirmed at subsequent visit)
 
• Time to ctDNA clearance
 
• Duration of ctDNA clearance
 
• Time to ctDNA recurrence
 
• Time to confirmed ctDNA recurrence
 
• Changes in variant allele frequencies (VAF) following treatment
 

To assess the relationship between treatment effect on DFS and treatment effect on ctDNA endpoints	ctDNA endpoints (as defined above) and DFS
To assess the association of TMB with efficacy of durvalumab compared with placebo, and other biomarker subpopulations	DFS, OS, and other efficacy endpoints in patients according to TMB in subpopulations including, but not limited to, PD-L1 TC≥1%, ctDNA endpoints, etc.


To investigate biomarkers in tumor and periphery at baseline, on treatment, post-treatment and/or at recurrence wherever feasible to identify markers related to disease, mechanism of action of the drug and/or their associations with response and clinical endpoints.
	
Exploratory markers, which may include, but are not limited to: tumor, immune, and/or stromal cell gene and protein expression profiles within the peripheral and tumoral compartments.
 
TMB and somatic mutations in tissue and/or blood/plasma.
 
Changes in RNA, DNA or protein
 
Attributes of tumor microenvironment that could be assessed using various methods which may include, but not limited to, high content imaging, multiplex RNA/DNA/protein analysis with spatial resolution such as Mass Spec or other technologies.

To evaluate patient-reported treatment-related symptoms using PRO-CTCAE                  To assess the patient's global impression of symptoms severity, and global treatment tolerability
	
Pre-specified items on the PRO-CTCAE
 
Patient global assessments

To explore the impact of treatment and disease
	
CCI, descriptor, and VAS

To assess alternative methodologies for determining MRD
	
MRD determinations in screened patients

To assess prognostic value of ctDNA quantification at baseline
	
ctDNA quantification vs binary MRD classification (+/-) to DFS and other efficacy endpoints

To assess prognostic value of MRD classification by comparing outcomes of randomized (MRD+) placebo-treated patients to those of patients in surveillance and/or observation
	
 
• MRD status as determined at screening and various timepoints post-curative intent therapy
 
• DFS and other efficacy endpoints
 
• Time from surgery to DFS
 
• Site of relapse
 
• Second primary NSCLC
 

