## 8 STUDY ASSESSMENTS AND PROCEDURES

*From CSP v2.0 implementation at site, please use Section 10 as a reference point for the study. This study has closed enrolment early and patients will either start open-label durvalumab or be discontinued from the study.*

*Study assessments are clearly indicated in Section 10. Assessments and reporting of adverse events (Sections 8.3 and 8.4) have been retained; these sections must be followed for AE assessments and reporting prior to patient starting open-label durvalumab treatment or discontinuing the study. Sections 8.6 and 8.7 have been retained as a reference for samples collected prior to CSP v2.0 implementation at site; please note that no additional samples will be collected from patients once they have discontinued the study or have started to receive open-label durvalumab. Sections 8.1, 8.2, and 8.5 below refer to the original study assessments and procedures; these sections are not applicable following implementation of CSP v2.0 but are included below for reference and data completion.*

Study procedures and their timing are summarized in the SoAs (Table 1, Table 2, Table 3, and Table 4).

The Investigator will ensure that data are recorded on the eCRFs. The RAVE Web Based Data Capture system will be used for data collection and query handling.

The Investigator ensures the accuracy, completeness, legibility, and timeliness of the data recorded and of the provision of answers to data queries according to the Clinical Study Agreement. The Investigator will sign the completed eCRFs. A copy of the completed eCRFs will be archived at the study site.

Immediate safety concerns should be discussed with the Sponsor immediately upon occurrence or awareness to determine if the subject should continue or discontinue study treatment.

Adherence to the study design requirements, including those specified in the SoA, is essential and required for study conduct.

All screening evaluations must be completed and reviewed to confirm that potential subjects meet all eligibility criteria. The Investigator will maintain a screening log to record details of all subjects screened and to confirm eligibility or record reasons for screening failure, as applicable.

Procedures conducted as part of the patient's routine clinical management (eg, blood count and imaging assessments) and obtained before signing of ICF1 and/or ICF2a may be

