### **8.3.7 Adverse events based on examinations and tests**

The results from the Clinical Study Protocol-mandated laboratory tests and vital signs will be summarized in the clinical summary report (CSR). Deterioration as compared to baseline in protocol-mandated laboratory values and vital signs should therefore only be reported as AEs if they fulfill any of the SAE criteria or are the reason for discontinuation of treatment with the IP.

If deterioration in a laboratory value/vital sign is associated with clinical signs and symptoms, the sign or symptom will be reported as an AE and the associated laboratory result/vital sign will be considered as additional information. Wherever possible the reporting Investigator uses the clinical, rather than the laboratory term (eg, anemia versus low hemoglobin value). In the absence of clinical signs or symptoms, clinically relevant deteriorations in non-mandated parameters should be reported as AE(s).

Deterioration of a laboratory value, which is unequivocally due to disease progression, should not be reported as an AE/SAE.

Any new or aggravated clinically relevant abnormal medical finding at a physical examination as compared with the baseline assessment will be reported as an AE unless unequivocally related to the disease under study, see Sections 8.3.9 and 8.3.10.

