#### **9.4.2.2 Safety assessments**

For the change from baseline summaries for vital signs, laboratory data, ECGs (to be administered at baseline and as clinically indicated), and physical examinations, the baseline value will be the latest result obtained prior to the start of study treatment.

QTcF will be derived during creation of the reporting database using the reported ECG values (RR and QT) using the following formula:

$$QTcF = QT/RR^{(1/3)} \text{ where RR is in seconds}$$

Corrected calcium product will be derived during creation of the reporting database using the following formula:

$$\text{Corrected calcium (mmol/L)} = \text{Total calcium (mmol/L)} + ([40 - \text{albumin (G/L)}] \times 0.02)$$

The denominator used in laboratory summaries will only include evaluable patients, ie, those who had sufficient data to have the possibility of an abnormality.

For example:

- If a CTCAE criterion involves a change from baseline, evaluable patients would have both a pre-dose and at least 1 post-dose value recorded.
- If a CTCAE criterion does not consider changes from baseline to be evaluable, the patient need only have 1 post-dose value recorded.

The denominator in vital signs data should include only those patients with recorded data.

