1.1.2 Secondary Objectives

Secondary/Safety objective:	Endpoint/variables:
To assess the safety and tolerability profile of durvalumab monotherapy compared to placebo	AEs, physical examinations, vital signs, and laboratory findings

AE Adverse event.

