4.2.9.5 Vital Signs

All vital signs data (SBP, DBP, pulse rate, temperature, respiratory rate and weight) will be listed only.

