6. CHANGES OF ANALYSIS FROM PROTOCOL

The following are changes from the planned analyses described in version 2 of the CSP.

Overall visit response table updated to more accurately reflect RECIST 1.1 evaluations and responses applicable to this study.

Except that change, this SAP has been produced in line with section 10.4 of CSP V2.0, which states:

“Under CSP v2.0, as a result of the decision by AstraZeneca to close enrollment to the study and end study assessments early, all analyses of the objectives and endpoints listed in Section 3 will be descriptive only and considered exploratory. Further details will be included in the SAP.”

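### Vital signs belong to the only secondary objective and the protocol says they will be summarized, but the SAP only lists them and does not declare the change

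*Protocol*

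**What the plan says.** Both documents carry one secondary objective. The SAP (1.1.2) words it as "To assess the safety and tolerability profile of durvalumab monotherapy compared to placebo", and the protocol (1.2 and Table 7) gives its variables as "AEs, physical examinations, vital signs, and laboratory findings".

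On reporting, protocol 8.3.7 states: "The results from the Clinical Study Protocol-mandated laboratory tests and vital signs will be summarized in the clinical summary report (CSR". It then draws a consequence: deterioration in these measurements "should therefore only be reported as AEs if they fulfill any of the SAE criteria" or if they are the reason for stopping treatment. The version 2.0 note at the head of protocol Section 8 says: "Assessments and reporting of adverse events (Sections 8.3 and 8.4) have been retained". Protocol 9.4.2.2 fixes a baseline "For the change from baseline summaries for vital signs, laboratory data, ECGs" and physical examinations, and sets the vital-sign denominator as patients with recorded data. Protocol 9.5.2 presents all safety data by arm.

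SAP 4.2.9.5 says: "All vital signs data (SBP, DBP, pulse rate, temperature, respiratory rate and weight) will be listed only". SAP Section 1 undertakes to describe in Section 6 any change to a protocol specification. Section 6 names one, the overall visit response table, and continues: "Except that change, this SAP has been produced in line with section 10.4 of CSP V2.0".

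**The concern.** The listing-only rule removes the output on which the protocol's adverse event rule rests. Investigators were told not to report most vital-sign deteriorations as adverse events because the values would be summarized. If the summary is dropped and the reporting rule stays, some changes appear in no by-arm figure.

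What is at stake is a limited part of the comparative safety objective. Blood pressure, pulse, temperature, respiratory rate and weight are scheduled at second screening, at every cycle and at the 4-week follow-up (protocol Tables 2 and 3). Blood pressure and pulse are also taken before, halfway through and at the end of the first infusion (protocol 8.2.4). To compare arms on any of these after baseline, a reader of the study report would have to work through a listing patient by patient.

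**Working it through.** No power, alpha or event figure enters this point. The check sets the current texts side by side.

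**Step 1. What by-arm output does each variable of the objective receive?** SAP 4.1 presents descriptive statistics by treatment group.

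| Variable | Route into the AE data (protocol 8.3.7) | Post-baseline by-arm output in the SAP |
|---|---|---|
| AEs | Direct | Tables in 4.2.9.1 and 4.2.9.2 |
| Physical examinations | A new or worsened clinically relevant finding is an AE unless clearly due to the disease | Through the AE tables (see also SAP 3.3) |
| Laboratory findings | Restricted to serious changes or those that stop treatment | CTCAE shift tables; liver, thyroid and renal threshold counts (4.2.9.3) |
| Vital signs | Same restriction as laboratory findings | None (4.2.9.5) |

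Laboratory findings and vital signs share the same AE restriction and the same reason for it. Only laboratory findings keep the summary.

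**Step 2. Where does a vital-sign change end up?**

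- Serious, or the cause of stopping treatment: reported as an AE and tabulated.
- Accompanied by signs or symptoms: the sign or symptom is the AE, and the measured value is supporting information.
- Part of an infusion-related or hypersensitivity reaction: an AE of special interest (protocol 8.3.12), tabulated under SAP 4.2.9.2.
- Asymptomatic, non-serious and not stopping treatment: in the listing only.

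The last group is the gap.

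**Step 3. Is the change declared?** By the rule in SAP Section 1 it belongs in Section 6, and it is not there. The SAP amendment history does record the move to a listing.

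**Step 4. Does the SAP give a reason?** For ECGs, SAP 4.2.9.4 does: they are collected only as clinically indicated. For vital signs, which are collected on schedule, no reason is given.

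**Step 5. Size.** SAP 1.2 expects about 30 randomized patients at 1:1, so 30 / 2 = about 15 per arm. A full by-visit table over the SAP Appendix A windows, (729 − 29) / 28 + 1 = 26 of them, would need 26 windows × 6 parameters × 2 (value and change) = 312 rows. A compact table would need 6 parameters × 5 (baseline, maximum, minimum, and the change to each) = 30 rows. First-infusion systolic pressure, diastolic pressure and pulse at 3 times add 3 × 3 = 9, for 39 rows in all.

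**The case against.** The best defence is that version 2.0 delegates this choice. Protocol 10.4 makes every analysis descriptive and exploratory and leaves details to the SAP. Protocol 9.5.2 leaves the end-of-study safety summaries to the SAP. SAP Section 4 allows data to be either summarized or listed. The SAP cut comparable output throughout: laboratory value and change-from-baseline summaries went, and overall survival is listed only. One can also read the retention of protocol 8.3 as keeping the site reporting rules rather than an output commitment.

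Part of this stands. The decision was deliberate and logged, and a full by-visit table at about 15 patients per arm, with numbers falling over time, would be poor value. But descriptive does not mean listing only, as the laboratory tables under the same objective show. And if the reporting rule in 8.3.7 is retained, the reason stated for it cannot simply be set aside: AE data already collected under that rule depend on the summary.

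A reader might also infer that the vital-sign windows in SAP Appendix A serve no output. The documents do not establish this. The appendix offers them as an example of a general windowing rule, and SAP 4.1.2 has listings show the values that contribute to each time point.

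**Conclusion.** The conflict holds on the current text. Vital signs are a named variable of the only secondary objective, the retained protocol text says they will be summarized, and the SAP plans no post-baseline by-arm summary and does not declare that in Section 6. The consequence is specific: asymptomatic, non-serious changes that do not stop treatment are neither tabulated nor normally recorded as AEs.

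A reader might go further and infer that the report will contain no vital-sign result at all. The documents do not support that. All values are listed, baseline weight is summarized (SAP 4.2.10), and serious changes, changes that stop treatment, associated symptoms and infusion reactions reach the AE tables.

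The impact is modest with about 30 randomized patients and descriptive aims. The change should be made because it is cheap and closes a real gap. Nothing else in the analysis depends on it. The verdict assumes that sites followed 8.3.7 as written and that vital signs were collected as scheduled until study assessments ceased under version 2.0.

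**What to change.** In SAP 4.2.9.5, add one by-arm descriptive table on the safety analysis set. For each of the six parameters, give the baseline value, the maximum and minimum on-treatment value, and the change from baseline to each. Add blood pressure and pulse before, midway through and at the end of the Cycle 1 infusion. Use patients with recorded data as the denominator (protocol 9.4.2.2). The baseline and on-treatment extreme-value conventions in SAP 4.1.1 and 4.1.2 already cover the derivations. Keep the listing; no by-visit table is needed.

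In SAP Section 6, state that the change-from-baseline summaries foreseen for vital signs in protocol 9.4.2.2 are reduced to this table. With the table in place, protocol 8.3.7 is met and needs no amendment.

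Declaring the listing-only choice in Section 6 without a table would repair the documentation but leave the gap in the AE data. The cost of the full fix is one table, about 39 rows, from data already collected. The downside is that it describes few patients.
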